6.3.2 Dose adjustments for QTcF prolongation

Not applicable

6.3.3 Follow-up for toxicities

If treatment is interrupted due to an AE or abnormal laboratory value, patients must be followed at least once a week for 4 weeks and subsequently at approximately 4 week intervals, until resolution or stabilization of the event, whichever comes first. If treatment is permanently discontinued due to an AE or abnormal laboratory value (that meets criteria for an AE or SAE), patients must be followed for at least 30 days following the last dose of treatment. All patients must be followed for an AE and SAE for 30 days following the last dose of treatment.

6.3.3.1 Follow up on potential drug-induced liver injury (DILI) cases

Increases in ALT and AST with an elevated total bilirubin can be seen in advanced stage HH, but is uncommon.

Increases in ALT and AST with an increased total bilirubin may be indicative of a potential DILI and should be considered as a clinically important event.

The threshold for potential DILI may depend on the patient's baseline AST/ALT and total bilirubin value; patients meeting any of the following criteria will require further follow-up as outlined below:

- Baseline normal ALT and AST and total bilirubin: AST or ALT > 3.0 x ULN combined with total bilirubin > 2.0 x ULN
- Elevated baseline AST or ALT or total bilirubin: [AST or ALT > 2 x baseline AND > 3.0 x ULN] OR [AST or ALT > 8.0 x ULN] combined with [total bilirubin > 2 x baseline AND > 2.0 x ULN]
- Normal ALT and AST with increased total bilirubin: rule out Gilbert's syndrome, defined by increased indirect bilirubin.

Medical review needs to ensure that liver test elevations are not caused by cholestasis, defined as alkaline phosphatase > 2.0 x ULN with R < 2 in patients.

Note: (R is calculated by ALT divided by alkaline phosphatase, using multiples of the ULN for both values. It denotes whether the relative pattern of ALT and/or alkaline phosphatase elevation is due to cholestatic ($R \le 2$), hepatocellular ($R \ge 5$), or mixed (R > 2 and < 5) liver injury.

In the absence of cholestasis, patients must immediately discontinue from study treatment and repeat LFTs as soon as possible, preferably within 48 hours from the awareness of abnormal results. Evaluation should include laboratory tests, detailed history, physical assessment and consideration of liver metastasis or new liver lesions, obstructions/compressions, etc.

1. Laboratory tests should include ALT, AST, albumin, creatinine kinase, total bilirubin, direct and indirect bilirubin, GGT, prothrombin time/INR and alkaline phosphatase.

Confidential

- 2. Collect detailed history, such as review of ethanol, concomitant medications, herbal remedies, supplement consumption, pre-existing liver conditions or risk factors.
- 3. Testing for acute hepatitis A, B, C or E infections and liver imaging (e.g. biliary tract) if warranted.
- 4. Additional testing for other hepatotropic viral infections (CMV, EBV or HSV), autoimmune hepatitis or consultation with a hepatologist for liver biopsy if clinically indicated.

All cases, confirmed on repeat testing, that meet the laboratory criteria defined above and have no other alternative cause for abnormal LFTs, must be considered "medically significant" and meeting the definition of SAE (Section 8.2.1) for reporting as an SAE using the term "potential drug-induced liver injury". All events should be followed with the outcome clearly documented.

6.4 Concomitant medications

6.4.1 Permitted concomitant therapy

The patient must be reminded to notify the investigational site about any new medications he/she takes after starting study drug. All medications (other than study drug) and significant non-drug therapies (including physical therapy, herbal/natural medications and blood transfusions) administered during the study must be listed on the Concomitant Medications or the Procedures and Significant Non-Drug Therapies eCRF.

6.4.2 Permitted concomitant therapy requiring caution and/or action

Concomitant administration of deferasirox and vitamin C has not been formally studied. Vitamin C up to 200 mg/day has not been associated with adverse consequences.

Caution must be exercised if taking deferasirox in combination with the following:

- Drugs with a known ulcerogenic potential, such as NSAIDs, corticosteroids, oral bisphosphonates, or anticoagulants which may increase the risk of gastrointestinal irritation and bleeding
- Deferasirox is a weak CYP3A4 inducer and may potentially decrease serum levels of substances metabolized through CYP3A4
- Deferasirox is a moderate inhibitor of CYP2C8 and may increase serum levels of substances metabolized through CYP2C8 (e.g. repaglinide, paclitaxel).
- Deferasirox can potentially increase the levels of substances metabolized through CYP1A2 (e.g. theophylline, clozapine, tizanidine). Monitor theophylline levels and consider theophylline dose reduction.

• Potent UGT inducers (e.g. rifampicin, phenytoin, phenobarbital, ritonavir) may decrease deferasirox concentration.

6.4.3 **Prohibited concomitant therapy**

- Aluminium-containing antacid therapies may bind to deferasirox.
- Bile acid sequestrants (e.g., cholestyramine, colesevelam, colestipol) decrease deferasirox systemic exposure.
- Other iron chelators (deferoxamine, deferiprone, deferasirox) during study treatment and Post-treatment Ocular Follow-up phases
- Any investigational drug other than study medication

6.4.4 Use of Bisphosphonates

Requires caution (See Section 6.4.2)

6.5 Patient numbering, treatment assignment or randomization

6.5.1 Patient numbering

Each patient is assigned a Subject Number (Subject No.) when enrolled for screening. It is retained as the primary identifier for the patient throughout his/her entire participation in the trial.

Upon signing the informed consent form (ICF), the patient is assigned to the Subject No. available to the investigator through the Clinical Data Management System interface.

The investigator or designated staff will contact the Interactive Response Technology (IRT) provider and register the patient. Once assigned, the Subject No. must not be reused for any other subject and the Subject No. for that individual must not be changed, even if the patient is re-screened. If the patient fails to be randomized or start treatment, the reason must be entered on the Screening Disposition page.

IRT must be notified within 2 days that the patient was not randomized.

6.5.2 Treatment assignment or randomization

Patients will be assigned to one of the two treatment arms (Section 4.1 and Section 6.1), deferasirox FCT or phlebotomy in a 2:1 ratio.

Randomization numbers will be generated using the following procedure to ensure that treatment assignment is unbiased. A patient randomization list will be produced by the IRT provider using a validated system that automates the random assignment of patient numbers to randomization numbers. These randomization numbers are linked to the different treatment arms, which in turn are linked to medication numbers. A separate medication randomization

list will be produced by or under the responsibility of Novartis Drug Supply Management using a validated system that automates the random assignment of medication numbers to medication packs containing the study treatment.

Prior to dosing, all patients who fulfill all inclusion/exclusion criteria will be randomized via IRT to one of the treatment arms. The investigator or his/her delegate will call or log on to the IRT and confirm that the patient fulfills all inclusion/exclusion criteria. IRT will assign a randomization number to the patient, which will be used to link the patient to a treatment arm and will specify a unique medication number for the first package of study treatment to be dispensed to the patient. The randomization number will not be communicated to the caller.

6.5.3 Treatment blinding

This is an open-label study so investigators, patients, and sponsor will have full knowledge of treatment allocation. To minimize the potential impact of treatment knowledge, no aggregated statistical analyses (efficacy or safety) shall be performed by treatment (other than analyses specified in the protocol) until the primary analysis is conducted.

6.6 Study drug preparation and dispensation

The investigator or responsible site personnel must instruct the patient or caregiver to take the study drugs as per protocol. Study drug will be dispensed to the patient by authorized site personnel only. All dosages prescribed to the patient and all dose changes during the study must be recorded on the Dosage Administration Record eCRF.

6.6.1 Study treatment packaging and labeling

Study treatment, deferasirox FCT, will be provided from the global clinical open supply and will be packaged and labeled under the responsibility of Novartis Drug Supply Management.

Study treatment labels will comply with the legal requirements of each country and will include storage conditions and a unique medication number (corresponding to study treatment and strength). They will supply no information about the patient. Responsible site personnel will identify the study treatment package(s) to dispense by the medication number(s) assigned by IRT to the patient. Site personnel will add the patient number on the label. If the label has 2 parts (base plus tear-off label), immediately before dispensing the package to the patient, site personnel will detach the outer part of the label from the package and affix it to the patient's source document.

Study treatments	Packaging	Labeling (and dosing frequency)
deferasirox FCT	Tablets in bottles	Labeled as 'ICL670'
		Study treatment packaging has a 2-part label.

6.6.2 Drug supply and storage

Study treatments must be received by designated personnel at the study site, handled and stored safely and properly, and kept in a secured location to which only the investigator and designated site personnel have access. Upon receipt, the deferasirox FCT should be stored according to the instructions specified on the drug labels.

6.6.3 Study drug compliance and accountability

6.6.3.1 Study drug compliance

Compliance will be assessed by the investigator and/or study personnel at each patient visit. Information provided by the patient and/or caregiver will be captured in the Drug Accountability Form.

6.6.3.2 Study drug accountability

The investigator or designee must maintain an accurate record of the shipment and dispensing of study treatment in a Drug Accountability log. Drug accountability will be noted by the field monitor during site visits and at the completion of the study. Patients will be asked to return all unused study treatment and packaging on a regular basis, at the end of the study or at the time of study treatment discontinuation.

At study close-out and as appropriate during the course of the study, the investigator will return all used and unused study treatment, packaging, drug labels, and a copy of the completed Drug Accountability log to the Novartis monitor or to the Novartis address provided in the investigator folder at each site.

6.6.3.3 Handling of other study treatment (phlebotomy)

Patients randomized to the phlebotomy arm will go to a therapeutic phlebotomy center or hospital to receive treatment at a frequency that the investigator prescribes. The investigator or designee must collect an accurate record of the name of facility, the date of phlebotomy, hematocrit level prior to phlebotomy and amount of blood withdrawn at each treatment. This information must be captured in the source document at each visit and recorded on the eCRF.

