2.5 Rationale for choice of comparators drugs

The control arm is phlebotomy which is the standard of care for removing excess iron in nonanemic patients with HH. Most have unimpaired erythropoiesis so as blood is extracted, bone marrow is stimulated to make new red cells. Iron stores are reduced when iron is transported to make hemoglobin. Depending on the hematocrit, each unit of blood (typically 500 mL) contains 200-250 mg iron and removal by phlebotomy decreases the ferritin level by approximately 30 μ g/L (Bacon 1997). When SF is above normal, consensus opinion is that there is a benefit in early iron removal on a weekly or biweekly basis until iron stores are in the normal range (SF = 50-100 μ g/L), then thereafter, every two to four months to prevent re-accumulation of iron absorbed from a regular diet (EASL 2010, Tavill 2001). Although there are no evidence-based studies, SF is the accepted standard for initiating and monitoring response to achieve a SF \leq 100 μ g/L, which is used as the primary endpoint of this study. Phlebotomy will be conducted at a frequency determined by the investigator's clinical practice.

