5.2 Inclusion criteria

Written informed consent must be obtained prior to any screening procedures.

Patients eligible for inclusion must meet **all** following criteria prior to receiving study treatment:

- 1. Male or female \geq 18-years-old
- 2. Documented genotype testing confirming homozygous for the C282Y mutation (C282Y/C282Y)
- 3. Transferrin saturation \geq 45% (at either screening visit)
- 4. Serum ferritin (SF) \geq 500 µg/L (at either screening visit)

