Patients should not make up missed doses. A missed dose is when the full dose is not taken within 8 hours of the usual time of the daily dose. Omit that day's dose, and resume with the next scheduled dose.

Dose adjustments for safety are allowed at any time and must be in increments or decrements of 3.5 or 7 mg/kg/day. For this study, the maximum dose of deferasirox FCT is 14 mg/kg/day.

Patients randomized to phlebotomy will receive treatment at a frequency determined by the treating physician's judgment for optimal iron control. Phlebotomy must be interrupted when a patient achieves the target SF $\leq 100 \ \mu$ g/L. Treatment may be re-initiated when SF $> 100 \ \mu$ g/L.

Patients randomized to deferasirox FCT are not allowed to receive phlebotomy during the study treatment.

Patients randomized to the deferasirox FCT arm who discontinued from treatment may receive phlebotomy during Post-treatment Ocular Follow-up at a frequency determined by the physician.

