6.3 Dose modifications

6.3.1 Dose modification and dose delay

For patients who do not tolerate the protocol-specified dosing schedule, dose interruptions and/or reductions are either recommended or mandated in order to allow patients to continue the study treatment of defension FCT.

These dose modifications are summarized in Table 6-2. Deviations from the mandatory dose interruptions and/or reductions are not allowed. Permanent treatment discontinuation of deferasirox FCT is mandatory for specific events indicated in Table 6-2 or listed in Section 7.1.5.

These dose changes must be recorded on the Dosage Administration Record eCRF. It is important to keep an accurate dose adjustment records to enable an adequate evaluation of exposure.

Phlebotomy will be conducted at a frequency determined by the treating physician's clinical judgement for optimal iron control. The name of the facility, the date of phlebotomy, hematocrit level prior to phlebotomy and amount of blood withdrawn must be captured in Phlebotomy Record and local lab eCRFs. Phlebotomy must be interrupted when SF $\leq 100 \mu g/L$ and may be resumed when SF $\geq 100 \mu g/L$.

Novartis Amended Protocol Version 01 (Clean)

Table 6-2 Criteria for dose reduction / interruption and re-initiation of deferasirox FCT

Dose modifications for ICL670F2203		
Serum Ferritin (SF)		
After an initial starting dose (7 mg/kg/day) for 3 months (12 weeks), dose may be adjusted based on SF level. Dose increase cannot be more than 3.5 mg/kg/day at each adjustment.		
<300 µg/L	Decrease to 3.5 mg/kg/day	
300-1000 μg/L	Maintain 7 mg/kg/day	
>1000-2000 µg/L	Increase to 10.5 mg/kg/day	
>2000 µg/L	Increase to 14 mg/kg/day (higher doses are not allowed.)	
SF ≤ 100 μg/L at any time	Interrupt deferasirox FCT	
SF \geq 300 µg/L after dose interruption	Re-initiate deferasirox FCT 3.5 mg/kg/day. If SF continues to increase, increase to 7 mg/kg/day (maximum dose for maintenance phase).	
Body Weight		
Increase/decrease if weight changes >10% compared to baseline weight or weight at last dose adjustment due to a change in weight	Dose of study medication will be adapted using Dosing Table (provided in Appendix 14.1) When weight changes >10% compared to baseline weight or weight at last dose adjustment due to a change in weight, re-calculate dose. Smaller variations in weight (<10%) do not require dose adjustments.	
Investigations (Renal)		
Serum creatinine		
Single increase	Maintain dose and repeat assessment at next visit.	

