#### 2.6.7 Laboratory Data

On analyzing laboratory, data from all sources (central and local laboratories) will be combined. The summaries will include all assessments available for the lab parameter collected no later than 30 days after the last study treatment administration date (see Section 2.1.1).

The following summaries will be produced for hematology, urinary, and biochemistry laboratory data (by laboratory parameter and treatment):

- Descriptive Statistics for lab results and change by from baseline time point and treatment arm
- Shift tables using notable/extended ranges to compare baseline to the worst on-treatment value for key lab parameters (see Table 2-1)
- Shift tables using the low/normal/high/(low and high) classification to compare baseline to the worst on-treatment value.
- Trends of key lab parameter values over time (baseline and selected on-treatment timepoints) will be displayed via boxplots based on time windows and corresponding tables displaying the statistics used for the box plots by the selected time points.

The following listings will be produced for the laboratory data:

- Listings of all laboratory data, with classification relative to the laboratory normal range.
- Listing of all lab abnormalities based on notable/extended ranges

Parameter	Criteria
Absolute neutrophils	$< 1.5 \times 10^{9}$ /L (extended range $< 0.5 \times 10^{9}$ /L)
Platelets	$< 100 \times 10^{9}$ /L (extended range $< 50 \times 10^{9}$ /L)
Hemoglobin	< 100 g/L
ALT and AST	$> 5 \times$ ULN and $> 2 \times$ baseline (extended range $> 10 \times$ ULN and $> 2 \times$ baseline)
Total bilirubin	> 2 x ULN
Serum creatinine	> 33% increase from baseline and > ULN at 2 consecutive measurements at least 7 days apart
Creatinine clearance	< 60 mL/min at 2 consecutive measurements at least 7 days apart (extended range < 40 mL/min at least 7 days apart)
Urinary protein/creatinine ratio*	$\geq$ 1.0 mg/mg at 2 consecutive measurements at least 7 days apart

 Table 2-1 Definition of notable/extended ranges for key safety laboratory parameters

Novartis	Confidential	Page 29 of 36
SAP Amendment 1		Study No. CICL670F2203

\* If the unit of the parameter (Urinary protein/creatinine ratio) is in mg/mmol then will have to use a conversion factor as 0.00885 to convert into mg/mg unit for further derivation.

For all analyses, creatinine clearance will be re-derived using the Cockcroft-Gault equation described in Section 5.2.1.

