# 5.2.2 Multiple Assessments Within Post-Baseline Visits

All scheduled/unscheduled assessments should be assigned to time windows. In case of multiple values per window, the one closest to the planned visit date should be used. If 2 values are equidistant to the planned visit date, the selection should be made by selecting the one assessed by central (if any) and otherwise - for multiple central assessments equidistant to the planned visit - the last value. When multiple values are reported on the same day then the average value is used in analyses.

For worst post-baseline assessment, all on-treatment values are considered regardless of time windows. All unscheduled and repeat measurements will be included in listings.

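### Local hematocrit taken before each phlebotomy is pooled into the worst-value shift table, so that table samples the control arm more densely than the deferasirox arm

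*Protocol*

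**What the plan says.** **Collection.** Protocol 6.6.3.3 asks for "hematocrit level prior to phlebotomy and amount of blood withdrawn at each treatment". Protocol 6.3.1 adds the destination: "hematocrit level prior to phlebotomy and amount of blood withdrawn must be captured in Phlebotomy Record and local lab eCRFs". The value therefore enters the database as local laboratory data as well as a detail of the procedure.

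**Who has it.** Protocol 6.1.1: "Patients randomized to deferasirox FCT are not allowed to receive phlebotomy during the study treatment". The frequency in the control arm is left to the physician. Protocol 2.5 describes the consensus as "early iron removal on a weekly or biweekly basis" until iron stores are in the normal range.

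**Common schedule.** Table 7-1 gives both arms the same hematology visits, and Table 7-3 lists hematocrit as a hematology parameter.

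**Analysis.** SAP 2.6.7 states that "data from all sources (central and local laboratories) will be combined" and plans, for each hematology parameter, a shift table from baseline to the worst on-treatment value in low/normal/high classes. SAP 5.2.2 states: "For worst post-baseline assessment, all on-treatment values are considered regardless of time windows". SAP 2.3.1 also lists the hematocrit with each phlebotomy. Nothing in either document keeps these values out of the laboratory summaries.

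**The concern.** The lowest of many readings tends to be lower than the lowest of few, even when the underlying hematocrit is the same. If one arm adds a reading at every treatment and the other does not, a worst-value table by arm mixes two things: the real effect of removing blood, and the effect of looking more often. The table does not let a reader separate them.

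Low hematocrit is a directly expected consequence of phlebotomy. Laboratory abnormalities in both arms are part of a stated secondary objective. In an open-label study, an artefact that counts against the control arm should be removed when this is easy to do.

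**Working it through.** The documents give no figure for hematocrit ascertainment, so there is none to reproduce. The check counts values per patient and then asks what the difference does when there is no true difference between arms.

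**1. Scheduled values, both arms.** Week 2, plus Weeks 4 to 104 every 4 weeks (26 visits), gives 27 post-baseline samples.

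**2. Phlebotomies to target.** Protocol 2.5 says that "removal by phlebotomy decreases the ferritin level by approximately 30" µg/L per unit. Entry requires ferritin of at least 500 µg/L.
- From 500: (500 − 100)/30 = 13.3, so 14 procedures.
- From 1000: (1000 − 100)/30 = 30 procedures.

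The reading before the first procedure can serve as baseline (SAP 2.1.1), which leaves 13 and 29 post-baseline readings.

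**3. Remove draws that fall in a scheduled-visit week.**

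| Start ferritin (µg/L) | Interval | Readings | In visit weeks | Extra | Total |
|---|---|---|---|---|---|
| 500 | biweekly | 13 | 7 | 6 | 33 |
| 500 | weekly | 13 | 4 | 9 | 36 |
| 1000 | biweekly | 29 | 15 | 14 | 41 |
| 1000 | weekly | 29 | 8 | 21 | 48 |

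Same-day values are averaged under SAP 5.2.2, but a draw on another day of the visit week would still count. Counting every reading gives upper totals of 40 and 56. Maintenance phlebotomies are not included.

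**4. Chance of at least one low value, same true hematocrit.** Assumed: mean 44, between-patient SD 2.5, within-patient SD 1.3, lower limit 39. With b ~ N(0, 2.5²),

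P(n) = E_b[1 − (1 − Φ((39 − 44 − b)/1.3))^n].

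The implied within-patient correlation is 6.25/(6.25 + 1.69) = 0.79.

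| n | P(any low) | Relative to 27 |
|---|---|---|
| 27 | 17.6% | 1.00 |
| 33 | 18.7% | 1.06 |
| 36 | 19.2% | 1.09 |
| 41 | 19.9% | 1.13 |
| 48 | 20.7% | 1.18 |

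In an arm of 50, (18.7% − 17.6%) × 50 = 0.5 and (20.7% − 17.6%) × 50 = 1.6 patients. At the upper totals of 40 and 56 the model gives 19.7% and 21.6%.

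**5. Sensitivity to correlation.** Assumed 1% risk per value, Gaussian model with within-patient correlation ρ:

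| ρ | n = 27 | n = 36 | n = 40 | n = 56 |
|---|---|---|---|---|
| 0 | 23.8% | 30.4% | 33.1% | 43.1% |
| 0.5 | 12.5% | 14.7% | 15.5% | 18.3% |
| 0.8 | 6.1% | 6.8% | 7.0% | 7.9% |

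**6. Unequal time on treatment.** Under SAP 2.1.1 the on-treatment period ends 30 days after the last phlebotomy. A control patient who stops for good after 14 weekly procedures reaches day 13 × 7 + 30 = 121. That covers 5 scheduled visits (Weeks 2, 4, 8, 12, 16), so at most 5 + 13 = 18 values. P(18) = 15.5%, below the 17.6% for a deferasirox patient treated for the full 104 weeks.

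**The case against.** **Entry into the table is inferred.** A low/normal/high class needs a reference range. Phlebotomy takes place at a phlebotomy center or hospital, and the documents mention collecting local ranges only for the France-specific creatinine samples (Protocol 7.2.2.6.3). Values without a range may drop out. This stands, so the point is conditional. It also shows that a stated rule is needed.

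**The extra count is easily overstated.** Draws can fall on visit days or at baseline, and the on-treatment period can end early. This stands and is why steps 3 and 6 are there. An early end is less likely in the control arm, because phlebotomy may restart above 100 µg/L and deferasirox only at 300 µg/L or more (Protocol 4.1).

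**Taking every on-treatment value is a conservative safety rule, and it applies to both arms.** Local tests are allowed in either arm, and interruptions for abnormal values trigger weekly follow-up (Protocol 6.3.3). A patient who leaves deferasirox and is bled within 30 days could also add a value. These are occasional. A required reading at every treatment in one arm is systematic.

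**By-visit summaries are already protected.** SAP 5.2.2 takes the value closest to the planned date. This stands, and no change is asked for there.

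**A stronger reading is tempting.** With independent readings, the 1% row of step 5 suggests a jump from 24% to 33% or 43%, and a reader might infer that deferasirox will look better tolerated overall. The documents do not support that. Repeated hematocrits in one patient are not independent. Table 2-1 of the SAP sets a notable range for hemoglobin and none for hematocrit, and only hematocrit is required before phlebotomy. Some of any observed excess will be the true effect of blood removal.

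**Conclusion.** The point holds, within limits. As written, the SAP lets local pre-phlebotomy hematocrit into a between-arm worst-value table. Where those values can be classified, the control arm is sampled more densely and, for equal time on treatment, shifts to low are over-counted there.

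The size is an assumption, because the documents give neither the risk per value nor the correlation. Under the model in step 4, without draws in visit weeks, the relative excess is about 6 to 18%, or roughly 0.5 to 1.6 patients in 50. The direction is firm only for equal time on treatment and can reverse when a control patient stops early.

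Only the descriptive hematocrit low/normal/high table is affected. The hemoglobin notable range and the primary and key secondary endpoints are not.

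**What to change.** Add to SAP 2.6.7 or 5.2.2 a rule to this effect: for hematocrit, the between-arm shift table from baseline to worst value uses only central-laboratory samples from the Table 7-1 visits; local pre-phlebotomy values appear in the phlebotomy listing of SAP 2.3.1 and in a separate control-arm summary.

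Both arms then have 27 scheduled post-baseline values over 104 weeks. With equal true risk and equal time on treatment, the model gives 17.6% in each, so the excess from extra sampling is zero. Differences in time on treatment would remain.

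The cost is one sentence and a data filter, with no change to procedures or data collection. The downside is that a low value seen only locally appears in the control-arm summary or listing and not in the between-arm table.
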